2.4.2.25 Technical training and assessment

Prior to each subject using the SCS-LLA system unsupervised in the community outside of the lab environment, they will undergo training with lab staff on the proper use of the system, including techniques for donning and doffing, proper operation, calibration, and approaches for responding to system errors. Subjects will be instructed on various operating techniques, including:

- Connecting each component of the system and managing cables to avoid tangling or snagging on environmental hazards.
- Charging external batteries and connecting them to the Nomad
- Turning the system on and off and switching between operating modes (e.g. standby, calibration mode, active/stimulation mode)
- (Optional) Operating the smartphone application and using it to understand system state information (e.g. battery status) and control system parameters (e.g. enter calibration state, adjust peak stimulation intensity)
- Calibrating the system
- Responding to various error states (e.g. low battery, no stimulation, unexpected stimulation)

Before subjects are cleared for unsupervised community use of the system, lab staff will evaluate their understanding of system operations and approaches for responding to system error states, using the checklist in **Appendix E**. Supervised technical training may occur in the lab environment as well as during the two-week community use trial; however subjects will not be cleared for unsupervised community use until they have successfully demonstrated understanding of safe operating principals of the system.

2.4.2.26 Community use of SCS-LLA system

Subjects may participate in up to two weeks of community use of the SCS-LLA system and sensors applied to the exterior of their own prosthetic limb, including up to one week of unsupervised community use. Initially, during a period lasting no more than two weeks, subjects will engage in supervised community use of the system to gain experience with its operation and understanding of how to don/doff the system and how to respond to error conditions. After successfully completing clinic-based prosthetics training and assessment (Section 2.4.2.23) and technical training and assessment (Section 2.4.2.24), subjects will be cleared to participate in up to one week of unsupervised community use of the system. The total duration of supervised and unsupervised community use will not last longer than two weeks. During community use of the SCS-LLA system, data will be automatically collected by the external system. These data may include, but are not limited to, time of use, system state and error information, button presses, all sensor signals recorded by the system, and the timing and amplitude of all stimulation pulses delivered by the system. All data will be stored in a password protected file system inside the portable stimulation system (See Section E for more information). During the community use trial, subjects may also participate in lab-based testing such as balance and gait assessment, measurement of phantom limb pain, or sensory psychophysics.

2.4.2.27 Removal of SCS leads

After completion of testing and no later than 90 days after device placement, the SCS leads will be removed. Within two weeks prior to removal, at physician discretion, we may do other bloodwork, such as a complete blood count with differential and platelets; a prothrombin time and international normalized ratio; an activated partial thromboplastin time; iron, prealbumin, albumin, and a vitamin D 25-OH screen for deficiency/toxicity pre

explant based on physician discretion. A MRSA screen will be also be done to determine what antibiotics will be used during the procedure.

The subject will be taken to the procedural room or operating room at UPMC Mercy and placed on their stomach. As with implantation, an anesthesiologist may administer a mild anesthetic or general anesthesia. Prophylactic antibiotics (cefazolin and/or vancomycin, depending on MRSA status) will be intravenously administered approximately 30 minutes before the procedure. The sterile dressings for both the lead exit site and needle entry sites will be removed. We will apply sterile prep and drape to both the lead exit site and the needle entry site. The study neurosurgeon will then use a scalpel to open each of the needle entry sites. He will use surgical equipment to bluntly dissect at each level to the thoracolumbar fascia. Each of the anchoring devices attached to the percutaneous leads will be removed. The percutaneous leads will be removed from the epidural space and skin exit site. A study physician will inspect each lead to ensure that it is intact and was completely removed from the body. If there are any concerns about incomplete removal, fluoroscopic imaging can be used intraoperatively to visualize the epidural space and guide decisions about next steps, which will be determined by the neurosurgeon (e.g. additional surgical dissection to remove the remaining portion of the leads). The neurosurgeon and/or a neurosurgery resident will suture each of the needle entry sites in the skin and subcutaneous tissues; a sterile dressing will be applied to the area. The patient will be taken to recovery. This procedure is commonly performed at the end of percutaneous SCS trials and has a low rate of complications.

2.4.2.28 Lead removal follow-up and monitoring

We will monitor participants following lead removal to ensure healing of the lead removal site and to track any remaining changes in sensation or pain. A research team member will contact the participant once within 48 hours and again within one month of electrode removal to discuss changes in sensations associated with phantom limb pain. Research staff will also ask the participant questions regarding general wellness and if they are experiencing any side effects associated with lead removal and infection, including bleeding, redness, swelling, or fever. Additionally, after the lead removal procedure and follow-up call, the participant will meet with a study physician. The timing of this visit is at the discretion of the physician but will be within three weeks after explantation. At this visit, the physician will remove any remaining sutures and examine the removal site for proper healing and signs of infection. Any cases of suspected of infection will be discussed with Infectious Disease and study physicians will follow all Infectious Disease directives. A neuropsychologist will also have a follow-up evaluation approximately 3-4 weeks after explant. A neuropsychologist will evaluate the participant's psychological state at this time to determine if a referral for further clinical help during the transition period following explant is necessary.

2.5 Study outcome evaluations

2.5.1 Study endpoints

The SCS leads will be removed no later than 90 days after implantation. The primary safety endpoint will be that there are no serious device-related adverse events. The secondary safety endpoint will be to determine the type and frequency of device-related

adverse events measured of the 90-day period following implantation. The primary efficacy endpoint for this study will be demonstration of the ability to evoke sensations localized to at least three focal regions of the missing foot and shank (e.g. lateral forefoot, medial forefoot, and heel). The secondary efficacy endpoints will be an improvement in balance control and gait stability and a reduction in phantom limb pain. Balance control and gait stability will be measured by a 10-point improvement in the Sensory Organization Test or a 6-point improvement in Functional Gait Assessment. A reduction in phantom limb pain will be measured by a 5-point improvement in the McGill Pain Questionnaire.

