
1.3 Objectives of the clinical investigation

The proposed clinical investigation is a feasibility study directed toward the following aims:

Specific Aim 1: Demonstrate the safety of the SCS-LLA system over a period of up to 90 days. We will monitor adverse events throughout the study, and these results will provide supporting data for future studies with larger cohorts and a fully implanted SCS system.

Specific Aim 2: Characterize the sensations evoked by lumbar epidural spinal root stimulation in lower-limb amputees.

- **Specific Aim 2a:** Quantify the threshold (minimum charge and pulse rate) stimulus required to evoke sensory percepts and neurophysiological responses (e.g. reflexive EMG responses) during SCS, and monitor changes in those percepts and responses over time. These results will provide insight into the design requirements for a future SCS system, as well as a point of comparison among subjects and with other studies in the scientific literature. Additionally, the stability of the responses will provide insight into the feasibility of long-term use of the device.
- **Specific Aim 2b:** Evaluate the relationship between stimulation parameters (e.g. pulse width, pulse amplitude, stimulus location, etc.) and the modality and naturalness of perceived sensations. Lumbar SCS can evoke paresthesia referred to the amputated limb, but our goal is to produce meaningful (non-paresthetic) sensations. As we expect the stimulation parameters to have significant effects on the evoked sensations, we will perform standardized psychophysical examinations to determine the relationship between stimulation parameters and perceived sensations. These tests will be repeated at multiple points throughout the study to observe any changes that occur over multiple days of use.
- **Specific Aim 2c:** Document the subjective perception of lower-limb amputees of lumbar SCS for restoration of sensation. To achieve widespread adoption of a sensory neuroprosthesis, it will be crucial for amputees to perceive significant value from the device. As such, we will ask each subject to provide subjective feedback on their perceived utility of the sensory feedback provided by the device.

Specific Aim 3: Characterize the effects of lumbar SCS on phantom limb sensations and phantom limb pain in lower-limb amputees. This aim is secondary to the primary study goals in Aims 1 and 2, and as such, we will not exclude individuals that do not experience phantom limb pain.

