2.5.2 Study ending or halting due to safety

Subjects will be under medical supervision for the duration of this study and their health will be the top priority. Study physicians will be primarily responsible for evaluating a subject's medical condition. Study complications that may adversely affect a subject's health will consequently lead to the removal of the electrodes and ending of a subject's participation. Complications that could result in the removal of stimulation leads include:

- Lead migration that prevents the evocation of sensation in the missing limb
- Lead breakage
- Signs of systemic infection
- Unresolved local infection at the lead site
- Changes in subject's medical status that could affect eligibility
- Non-compliance with study procedures, including temperature monitoring, care of the implant sites, and attending testing sessions and clinical exams

We may halt the study and reevaluate our protocol and risk mitigation procedures due to the occurrence of multiple adverse events. Adverse events that could result in the halting of the study and re-evaluation of study protocol include:

- Two incidents of unresolved superficial infection resulting in lead removal
- One incident of deep infection
- One or more inpatient hospitalizations of subjects
- Two or more subjects who withdraw from the study due to worsening pain or intolerable dysesthesia
- One or more subjects who suffer a fracture due to falls related to the study interventions

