2.5.4 Outcome data and data analysis

The primary outcome measure of the study will be safety. We will track the rate of adverse events to monitor safety of the study. The primary efficacy outcome will be quantification and evaluation of the types of sensory percepts evoked by spinal root stimulation, as well as the anatomical locations to which those percepts are referred. Additionally, we will record any subjective changes in the perception of phantom limb sensations or phantom limb pain during and following spinal root stimulation. We will quantify differences in the ability to control a prosthetic limb with and without sensory stimulation. We will compare the balance and gait assessment scores of individuals using the SCS-LLA system and community-use of stimulation with the scores of subjects who underwent lab-only testing in our ongoing study to quantify the effects of extended access to the device.

New information will be learned with each participant, as this is a pilot study. Single-subject design statistical analyses will be used. Our main goals are to demonstrate device safety as well as the feasibility of using spinal root stimulation to evoke realistic sensory percepts referred to the foot and leg in individuals with lower-limb amputation, and to document any effects of that stimulation on phantom limb sensations and phantom limb pain. We will quantify the threshold for producing a just-noticeable sensory percept, as well as the relationships between stimulation parameters and evoked sensations when stimulating through individual electrodes or combinations of multiple electrodes.

To fulfill Specific Aim 1, we will document adverse events that occur during the study. We will report adverse events to the local Institutional Review Board and to the FDA in accordance with the respective reporting requirements. This documentation will serve as demonstration of the safety of the SCS-LLA system in this small sample.

To fulfill Specific Aim 2a, in which we quantify the threshold for evoking a sensory percept, we will use regression analysis to examine differences in stimulation thresholds related to a variety of factors. Examples of these factors include the anatomical location of each electrode (based on fluoroscopic imaging), level of amputation, time since amputation, level of pre-intervention phantom limb sensation and pain, and the thresholds of nearby electrodes.

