According to the PMA that covers the Abbott Medical Spinal Cord Stimulation System, the most common adverse event is lead migration, which occurs in 13.6% of patients. Even in the case where lead migration occurs, the medical risk to the subject is low, with the more likely result being a change in the anatomical location of the perceived sensations. Other common risks include seroma and bruising at the placement site. The lead anchoring procedure performed by the study physician and neurosurgeon will minimize this migration. Additionally, we intend to examine the stability of the neurophysiological response to stimulation over the course of the experimental session and the effects that stability may have on the perceived sensations. The tables included in the Abbott Medical Spinal Cord Stimulation System PMA (**Appendix C**) list the rates of complications. Placement of the Tuohy needle and spinal cord stimulator leads could potentially result in nerve damage that can cause neurological dysfunction, including paralysis. Additionally, it is possible that a tear in the dura could occur, resulting in a spinal fluid leak or hemorrhage (refer to **Appendix C**; risk: 0.5%). A spinal fluid leak can cause headaches and, in rare cases, may require surgery. The placement of these devices is common clinical practice for treatment of intractable lower back and limb pain, and complications are rare. There is a low risk of meningitis and infection at the electrode placement site as a result of lead placement, though the use of sterile technique during device placement makes this risk low (**Appendix C**; risk: 3.0%).

Steps taken to minimize these risks:

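### Both safety endpoints count only device-related events, a term the available text does not define, and the 90-day window can miss complications of lead removal

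*Combined protocol and SAP*

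**What the plan says.** Section 2.5.1 sets the primary safety endpoint as a zero-event rule: "The primary safety endpoint will be that there are no serious device-related adverse events". The sentence has no time window of its own. The secondary endpoint follows: "The secondary safety endpoint will be to determine the type and frequency of device-related" events, counted as "adverse events measured of the 90-day period following implantation".

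Other sections are wider. Specific Aim 1 (section 1.3) is to "Demonstrate the safety of the SCS-LLA system over a period of up to 90 days". Section 2.5.4 names safety as the primary outcome measure, tracks the adverse event rate without a relatedness limit, and says: "To fulfill Specific Aim 1, we will document adverse events that occur during the study". It treats that documentation as the demonstration of safety.

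Section 1.2 describes the device as the external stimulation and data acquisition system, the percutaneous leads and the sensors. Section 3.1 discusses general anesthesia, stimulation, lead placement, lead presence, sedation and lead removal under separate headings. Under placement it says: "Placement of the Tuohy needle and spinal cord stimulator leads could potentially result in nerve damage that can cause neurological dysfunction, including paralysis". On removal, section 2.4.2.27 says that "no later than 90 days after device placement, the SCS leads will be removed".

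**The concern.** The system cannot be used without one operation to place and anchor the leads and a second to remove them. If harm from those operations is recorded as procedure-related, it does not count against the endpoint meant to show that the system is safe. With about 10 subjects and a zero-event rule, the attribution of a single event can decide the result. The study is open-label, and the available text names nobody to judge relatedness and gives no rule for doing so.

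Aim 1 is also meant to support larger studies of a fully implanted system. Harm from implantation bears directly on that use, so a reader of the final report needs to see it in the headline safety result.

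**Working it through.** The plan gives no safety rate, margin or power to reproduce. The sample size in section 2.5.3 rests on feasibility alone. The check is therefore mainly a comparison of the texts.

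**Scope**

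| Place | Events covered |
|---|---|
| 2.5.1 primary | serious and device-related |
| 2.5.1 secondary | device-related |
| 2.5.4 outcome and Aim 1 | adverse events, no relatedness limit |

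**How a serious event would be classified**

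- *Pneumonia after general anesthesia* (section 3.1). This is not the stimulator, leads or sensors of section 1.2. It would most naturally be recorded as anesthesia-related, and the primary endpoint would be met.
- *Spinal fluid leak, nerve damage or infection.* Section 3.1 lists these under lead placement and again under lead presence, so either attribution can be defended.
- *Fall with fracture.* Section 3.1 ties falls to walking with the system. An assessor could blame the device, the training or the underlying amputation.

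**Window**

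The secondary endpoint covers days 0 to 90 after implantation. For an explant on day *d*, it covers 90 − *d* days of recovery. At the latest permitted day this is 90 − 90 = 0 days. Section 2.4.2.28 already schedules contact within 48 hours and within one month of removal, and a physician visit within three weeks. After a day-90 explant, these follow-ups come at or after the end of the window.

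**Scale: upper illustrations only**

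Inputs from section 3.1 (placement): dural tear 0.5%, meningitis or placement-site infection 3.0%. With independent subjects, P(at least one event) = 1 − (1 − p)^n.

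| Event | n = 10 | n = 15 |
|---|---|---|
| Dural tear | 1 − 0.995^10 = 4.9% | 1 − 0.995^15 = 7.2% |
| Infection | 1 − 0.97^10 = 26.3% | 1 − 0.97^15 = 36.7% |

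The n = 15 column relies on section 2.3.2, which lets up to 15 subjects undergo procedures. Section 2.5.3 caps that number at 10.

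These figures count every dural tear or infection. The gap concerns only the share *s* that is both serious and judged not device-related, so the relevant chance is 1 − (1 − s·p)^n. The documents give no *s*. For infection with n = 10:

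- s = 0: 0%
- s = 0.5 (an assumption): 1 − 0.985^10 = 14.0%
- s = 1: 26.3%

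Even these are upper values for a trial that meets its endpoint despite such an event, because the endpoint also requires no serious device-related event.

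**The case against.** The strongest reply is that a sensible assessor would call most of these events device-related. The 0.5% and 3.0% come from the complication tables of the device's own approval. Section 3.1 attributes infection during the study to leads protruding through the skin, and section 3.2 calls infection the primary risk of chronically placed electrodes. This stands against one tempting inference, that surgical events are plainly excluded from both endpoints. The text does not settle that. It leaves such events open to either attribution. Harm purely from anesthesia or sedation is the clearer omission, and the protocol gives no overall rate of serious harm from it.

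A reader might also see a contradiction with the halting list in section 2.5.2, which includes "One or more subjects who suffer a fracture due to falls related to the study interventions" and any inpatient hospitalization. That does not hold. The list is discretionary and may reasonably be wider than an endpoint, so a study could be paused for review while its endpoint is met.

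A third inference is that serious events would go unseen. They would not. Adverse events are documented and reported to the IRB and FDA, the DSMB weighs risk against benefit, and subjects are followed after explant. The study is descriptive with no safety hypothesis test, so the effect is on what the headline endpoint reports.

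Finally, the appendices (including the case report forms) and the text between sections 6.0 and 8.0 were not available. A definition of device-related there cannot be ruled out.

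**Conclusion.** The point holds as a gap in endpoint scope, definition and timing. As section 2.5.1 is worded, a serious event attributed to surgery or anesthesia leaves the primary safety endpoint met. A borderline event can be placed on either side with no stated rule. The secondary endpoint can miss complications of a late explant on timing alone.

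The size cannot be estimated from the documents. The range 4.9% to 36.7% shows only that a dural tear or infection is not remote in 10 to 15 subjects. It assumes independent subjects and the protocol's placement rates, and it does not measure the gap. Severity is modest because surveillance and reporting are intact. The conclusion also assumes that no definition exists in the material not available. If one does, the scope part is settled by citing it in 2.5.1, provided it covers the procedures. The window would still need changing.

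**What to change.** In section 2.5.1:

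1. Restate the primary safety endpoint as no serious adverse events related to the device, the stimulation, the lead placement or removal procedure (including anesthesia or sedation), or study-directed use of the system.
2. Give the secondary safety endpoint the same scope.
3. Run both endpoints through the existing post-explant follow-up of about one month (section 2.4.2.28), in place of 90 days after implantation.
4. Tabulate device-related and procedure-related events separately, alongside the all-event documentation of section 2.5.4. A reader can then still see the device's own contribution.

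The cost is small. The events are already documented and the follow-up contacts already scheduled, so no new visits are needed. The safety result may look slightly less favourable. Event-by-event adjudication by the DSMB would be an added duty, since section 4.4 does not list it. The fix does not depend on it, because under the wider scope the choice between device and procedure no longer decides the primary result.

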Immediately following lead placement and up to 5 times per week for the following 90 days, experimental procedures will be performed. The day-to-day experimental procedures for each session will ultimately be decided by the PI, as they may depend on a variety of factors including progress towards our experimental goals, the current state of our technical setup (e.g. if hardware breaks and must be repaired), and the number of hours the subject is available on a given day. A typical day of testing might include psychophysical examination of sensations (e.g. receptive field mapping, measurement of threshold and just-noticeable difference) in the morning, followed by a lunch break, followed by x-rays and testing of the control of the prosthesis with sensory stimulation in the afternoon. Each testing session will be limited to no more than 8 hours, and will include breaks. Meals will also be provided. During experiments, SCS stimulation will either be delivered by an Abbott external stimulator or a current-controlled 32-channel neural stimulator (manufactured by Ripple, LLC; refer to **Section E** of this application for more detail).

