2.4.2.14 Weekly x-ray to document lead migration

Once per week for the first four weeks' post-implant and once every two weeks for the remainder of the 90 days, multi-view x-rays (including AP and lateral views) of the thoracic and/or lumbosacral spine will be taken to document the location of the leads and any movement that may have occurred. We will attempt to correlate movement of the electrodes with any documented changes in stimulation thresholds or the types of sensory percepts that are evoked by stimulation.

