The maximum amount of radiation exposure that participants will receive from each multi-view x-ray of the thoracic spine is 1 mSv, and the lumbosacral spine is 1.5 mSv. Participants will receive multi-view x-rays for the first four weeks following implantation, and then multi-view x-rays biweekly for the remainder of the study, for a total of eight x-rays and a maximum exposure of 20 mSv. This is a fraction of the annual radiation exposure (50 mSv) permitted to the most sensitive organs of radiation workers by federal regulations. There is no minimal level of radiation exposure that is recognized as being totally free of the risk of causing genetic mutations or cancer. However, the risk associated with the amount of radiation exposure that the subject will receive from these x-rays is considered to be low and comparable to everyday risks. To minimize radiation exposure, we will only collect both thoracic and lumbosacral x-rays if the leads cannot be visualized with only one of the two images.

Steps taken to minimize these risks:

Imaging studies are necessary to document any movement of the stimulator leads over the course of the study. The risk associated with the amount of radiation exposure that the subject will receive from these x-rays is below 50 mSv, which is the annual radiation exposure limit for radiation workers. At the end of the study, we will notify subjects of their effective radiation exposure dose during the study and will instruct them to notify their doctor of this dose prior to any additional imaging for 12 months following study participation.

3.2 Summary of risks and justification related to the use of spinal cord stimulation

The primary risk for a study of chronically placed electrodes is infection. However, current statistics show that this risk is quite low (6%). Infection risk is further minimized through the use of frequent checks by the physicians and study team, a specific wound/skin care procedure designed to reduce the chance of infection, and the administration of prophylactic antibiotics on the day of lead placement. The General Health Questionnaire mentioned previously also provides the study team with pertinent medical information, allowing us to exclude individuals who may be immunosuppressed and/or at a higher risk of infection.

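### The secondary safety endpoint closes 90 days after implantation, so delayed post-removal events count in full only for explants by about day 60 and not at all for a day-90 explant

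*Combined protocol and SAP*

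**What the plan says.** Section 2.5.1 sets the secondary safety endpoint as the type and frequency of device-related "adverse events measured of the 90-day period following implantation". Section 2.4.2.27 makes removal variable but capped: "After completion of testing and no later than 90 days after device placement, the SCS leads will be removed". Section 2.5.1 repeats the cap.

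Other sections indicate how long the leads are expected to stay in:
- Section 2.4.2.11: "up to 5 times per week for the following 90 days, experimental procedures will be performed".
- Section 2.4.2.14: x-rays weekly for four weeks, then "once every two weeks for the remainder of the 90 days".
- Section 3.1, on the spinal x-rays: "for a total of eight x-rays and a maximum exposure of 20 mSv".

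Section 2.4.2.28 then provides for safety follow-up after the leads are out: "A research team member will contact the participant once within 48 hours and again within one month of electrode removal". Staff ask about "side effects associated with lead removal and infection, including bleeding, redness, swelling, or fever". A physician also examines the removal site at a visit that "will be within three weeks after explantation".

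No section extends the secondary endpoint to cover this follow-up. Aim 1 (section 1.3) and section 2.5.4 do monitor and document adverse events across the whole study, and the primary safety endpoint (no serious device-related events) carries no time limit.

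**The concern.** The endpoint clock starts at implantation and stops at day 90, while the post-removal follow-up clock starts at explant. For late explants the two barely overlap. Section 3.1, under lead removal, names skin infection after implantation as a risk, and these are the events the follow-up contacts are meant to find.

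The same event is therefore handled differently according to explant date. An infection appearing 10 days after removal is counted if the leads came out by day 80 and omitted if they came out later. The uncounted time is longest for the longest implants, and section 3.1 says that infection risk may rise with implant duration. Aim 1 intends these results to support later, larger studies, so an incomplete frequency count would carry forward.

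A smaller related gap is that section 2.5.1 does not say whether events arising from the implant or explant procedure count as device-related.

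**Working it through.** The documents contain no power or precision calculation bearing on this point. The check is calendar arithmetic.

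**Inputs**
- Endpoint window: 90 days from implantation (2.5.1).
- Latest explant: day 90 (2.4.2.27, 2.5.1).
- Post-removal contacts: within 48 hours and within one month; physician visit within three weeks, or 21 days (2.4.2.28).
- Assumption: one month = 30 days, with 28 to 31 as the range.
- Goal of 10 completed subjects (2.3.2).

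**The plan's own x-ray figure.** Four weekly films, then one every two weeks:
- First film on day 7: days 7, 14, 21, 28, 42, 56, 70, 84. The next would be day 98, past day 90. Total 8.
- First film on day 0: days 0, 7, 14, 21, 35, 49, 63, 77. The next would be day 91. Total 8.

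Both give the stated eight films, and 8 × (1 + 1.5) mSv = 20 mSv, as section 3.1 states. The documents do not fix the first film's date, so the schedule ends at day 77 or day 84 on these two assumptions.

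**Post-removal days counted now.** For explant day E and follow-up length F:

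counted = max(0, min(F, 90 − E))

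With F = 30:

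| Explant day | Counted | Uncounted |
|---|---|---|
| 60 | 30 | 0 |
| 75 | 15 | 15 |
| 77 | 13 | 17 |
| 84 | 6 | 24 |
| 90 | 0 | 30 |

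A subject who completes the x-ray schedule therefore has at most 13 (last film day 77) or 6 (last film day 84) of 30 days counted.

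**Latest explant day with full coverage = 90 − F**
- One-month contact: 90 − 30 = day 60 (day 62 if F = 28, day 59 if F = 31).
- Three-week visit: 90 − 21 = day 69.
- 48-hour contact: 90 − 2 = day 88.

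These use the latest permitted date of each contact; an actual contact may fall earlier. A day-90 explant has no later day counted under any of these readings, although an event on the day of removal itself could still count.

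**Event 10 days after removal.** It is counted if E + 10 ≤ 90, that is, E ≤ 80.

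**Weight of one subject.** With 10 subjects, 1/10 = 10 percentage points on the proportion with an event, for each subject whose only event is uncounted.

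**Proposed window end = max(90, E + 30)**

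| Explant day | Window ends | Days added |
|---|---|---|
| 20 | 90 | 0 |
| 60 | 90 | 0 |
| 75 | 105 | 15 |
| 84 | 114 | 24 |
| 90 | 120 | 30 |

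No subject's window becomes shorter.

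**The case against.** The best defence is that nothing goes unseen. Adverse events are documented and reported for the whole study, post-removal contacts are scheduled, and late serious device-related events are not excluded from the primary endpoint. Only a descriptive count in a feasibility study of about 10 subjects is affected. This stands, and it is why the point is minor.

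A fixed 90 days also matches the framing of Aim 1 and gives every subject equal calendar time. That is a real advantage, but the window does not measure device exposure. A day-20 explant contributes 90 − 20 = 70 post-removal days and a day-90 explant contributes none.

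Several of the timing statements are upper limits, and leads may come out early once testing is complete or because of a complication. That is correct, so day 90 is not certain for any subject. Even so, the session period, the x-ray schedule, the 90-day testing portion in section 2.4.2.20 and the 90-day lead presence in section 3.1 all point to late explant as the planned course.

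Two cautions also stand. The infection-duration statement does not separate infection during implantation from infection starting after removal, so it does not show that the uncounted days carry more risk. And if explant-procedure events are not device-related, the window is not what excludes them. The 10-point figure likewise applies to a proportion of subjects, a denominator the endpoint does not define.

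**Conclusion.** The concern holds, as a minor design point. Applied as written, the secondary safety endpoint omits some or all of the delayed events that the planned follow-up is meant to detect whenever explant falls after about day 60 (day 59 to 62 for a month of 31 to 28 days), and all of them for a day-90 explant. For subjects who follow the x-ray schedule to its end, at least 17 or 24 of the 30 post-removal days go uncounted, depending on the assumed date of the first film. The calendar result is firm. How many events would be lost is unknown, because no post-removal rate is given. The effect is limited to one descriptive secondary endpoint and mainly to non-serious late events; it is not a gap in safety surveillance.

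**What to change.** In section 2.5.1:
- Run the secondary safety endpoint from the start of lead placement through the later of day 90 or 30 days after removal of the last lead. The last lead is the right anchor because section 2.4.2.15 allows removal at an infected site only.
- State that events related to the implant or explant procedure count.
- Report the implant period and the first 30 post-removal days separately. List any later events up to day 90 for subjects explanted before day 60.
- State that this window does not shorten the primary serious-event endpoint. Leave the study-long adverse-event documentation in sections 1.3 and 2.5.4 unchanged.

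In section 2.4.2.28, hold the last planned adverse-event contact at about day 30 after removal, so that the post-removal period is fully observed.

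The cost is mainly wording, since the contacts are already planned. Total observation would range from 90 to 120 days by explant date instead of a uniform 90, which the separate reporting makes visible. The final contact has a narrower target date, and the reported event frequency may be slightly higher.
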